## 12.0 Statistical Considerations

**Attrition and nonresponse.** Despite our efforts, some attrition and missing data are likely. The mixed model does allow missing data and provides valid results under the assumption of missing at random (MAR). MAR means that the missingness can be related to model covariates as well as observed values of the dependent variable and is sometimes termed "ignorable" missingness. As Molenberghs et. al. detail, MAR is a relatively weak and non-restrictive assumption about the missing data. Nonetheless, the possibility of non-ignorable missingness cannot be ruled out and so, as advocated by Molenberghs et. al., we will conduct sensitivity analyses using non-ignorable pattern-mixture and selection models to investigate the robustness of our conclusions across these different models for missing data. These sensitivity analyses apply to the both the longitudinal and EMA models that we have proposed. In particular, in the EMA context we will jointly model the outcomes and EMA prompt missingness, with random subject effects shared by both models. In this way, our model for the outcome will control for a person's propensity to miss EMA prompts.

**Power considerations.** The proposed sample size of 120 smokers was determined based on the primary aims. In all power calculations, we conservatively assumed an attrition rate of 10%, yielding a sample size of 108 at the end of the study. We will randomize 60 smokers to usual flavor SREC (N=54 at end) and 60 smokers to choice of flavor SREC (N=54 at end). The primary endpoint is the group difference in the rate of combustible cigarettes used at the 12-week timepoint. We will model this outcome across time in a mixed Poisson model. Based on data from our prior study of dual users of cigarettes and e-cigarettes and current experience, the average rate of smoking is expected to be between 11 to 15 cigs/day. With the proposed sample of 54/54 at the 12-week timepoint, we have power of .8 for a two-tailed hypothesis test to detect a relative risk of .75 (reduction to 8.2 cigs/day in the flavor choice group relative to 11 cigs/day in the usual flavor group or reduction to 11.25 cigs/day in choice vs 15 cigs/day in usual flavor). We note that these are conservative estimates of power as these calculations only consider data from the 12-week timepoint, whereas our model will include the longitudinal data from the 12 weeks. In addition, we expect significantly greater reductions in the flavor choice group than we are estimating here given expectations of greater engagement and adherence in the choice group, but these power considerations build in the likelihood that reductions are not sustained. Thus, we believe that these are conservative estimates. In terms of the binary outcome of abstinence at the final 12-week timepoint, we have power = 0.8 for a comparison of abstinence rates of 31.5%

(flavor choice) vs 10.% (usual flavor) for a two-tailed hypothesis test. Again, this is conservative as it is a two-tailed test and only considers data at the 12-week timepoint and attrition of 10%. Thus, we have good power to detect meaningful differences in both smoking rates and smoking/abstinence classification. In addition, given the ample EMA data, we will be able to examine how satisfaction/pleasure from SREC is associated with adherence to SREC and reduction in cigarette rate. For aim 2, which will examine associations between changes in SREC usage and change in health outcomes, again, we conservatively consider power at one timepoint. For this, with the sample size of 108 (allowing for 10% attrition), we can detect a correlation of .262 with power of .8 on a two-tailed hypothesis test. This level of association is between a small and medium effect size, and in line with correlations that we have observed in our prior studies.

For aim 3, in terms of the EMA data, given that we are including smokers who smoke 3+cigs/day; we are likely to have many events per day over the week to sample. Even with 3 smoke events/ day; plus 5 random a day – that is likely to give about 30 random events and at least 21 smoke events at baseline across 120 participants, providing ample data for within- and between-subject analyses. As an example, we can consider power for comparing responses from smoking reports to random prompts using simulation. Based on our current data, we assumed an intraclass correlation coefficient between 0.3 to 0.4, and considered power for a binary outcome (e.g., alone vs not alone). We simulated 1000 datasets and estimated a logistic mixed effects model including a random subject effect and fixed effect comparing random prompts and smoking reports. Power is determined as the proportion of datasets in which the null hypothesis of no difference between random prompts and smoking reports is rejected. Under these assumptions, power exceeded 0.8 for an odds ratio of 1.2.

For aim 4, during the switch week we are likely to see the same number of random events (and the SREC events and conventional cigarette events may both occur). Thus, we can examine what are the situations in which they still smoke or contexts in which they can switch. If we assume, conservatively, 20 smoking events and 10 SREC events, with 108 subjects (allowing for 10% attrition) and an ICC between 0.3 and 0.4, we can detect an odds ratio of 1.25 with power = .8 on a two-tailed .05 test. Thus, we have excellent power to detect rather small differences for within-subject comparisons involving cigarette vs SREC reports, even with a modest number of SREC events per person. Power for comparisons to random prompts will be even better.

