**AIM 1: Examine whether conventional cigarette smokers can significantly reduce their combustible cigarette use by switching to SREC.** We hypothesize that smokers randomized to the flavor choice condition will show significantly greater reductions in combustible cigarette use than smokers in the usual flavor condition. We will assess changes in use of products over a 12-week trial. We will also examine moderators of effects, including sex, baseline menthol cigarette use (not SREC flavor), and nicotine dependence level at baseline.

**AIM 2: Examine whether reductions in conventional cigarette use and uptake of SREC are associated with changes in health and biomarker variables.** We will have longitudinal measures of all

combustible tobacco products as well as SREC use and will examine how these longitudinal changes in patterns of use are associated with changes in expired air carbon monoxide (CO); blood pressure; heart rate; weight; respiratory symptoms; withdrawal symptoms; and nicotine dependence. We hypothesize that smokers who show more complete substitution will show greater reductions in CO and respiratory symptoms.

**AIM 3: Examine smokers' subjective responses to SREC in real time, as they are used, and whether these responses are associated with cigarette reduction.** We hypothesize that smokers in the flavor choice condition will show more adherence to the switching intervention and report higher levels of satisfaction, pleasure, and mood enhancements than smokers in the usual flavor EC condition and that these responses will predict level of cigarette reduction. Data will come from EMA measures and daily surveys. We will also descriptively examine how SREC flavor may be associated with subjective responses.

**AIM 4: Examine how patterns of use (e.g., contexts, timing) and subjective experience with SREC differ from conventional cigarette use, and whether differences are associated with success in switching to SREC.** These within-subject analyses will use EMA data. We hypothesize that subjects who have fewer differences in patterns and experiences between cigarettes and SREC will reduce cigarettes more and maintain SREC use longer.

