**Aim 3: Examine smokers' subjective responses to SREC in real time, and whether these responses are associated with cigarette reduction.** Levels of satisfaction, pleasure, mood change following use, and withdrawal symptoms will be assessed via EMA during the second week of SREC use. Level of satisfaction, pleasure, and mood will be assessed following each use of SREC (event report), and withdrawal symptoms will be assessed both during random times and following SREC use. We will also descriptively examine how the SREC flavor may be associated with adherence and overall level of subjective responses. We will use linear mixed models to compare groups in terms of the EMA subjective reports and withdrawal symptoms. Also, using the empirical Bayes estimates from these linear mixed models of EMA-reported subjective experience and withdrawal, we will examine whether these predict longitudinal changes in cigarette use over the following weeks, which will be modeled using a Poisson mixed model including effects of group, time (and group by time if significant). We will specifically examine the effects of satisfaction and withdrawal on cigarette use, both as main effects and as interactions with time if significant. Again, we will follow the resampling approach to account for the uncertainty of the empirical Bayes estimates.

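### The only power figure given for Aim 3 (above 0.8 at an odds ratio of 1.2) is a within-person, baseline-week example. It does not apply to Aim 3's comparison of flavor groups or to its person-level prediction.

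*Combined protocol and SAP*

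**What the plan says.** Section 3.0 (Aim 3) hypothesises that the flavor-choice arm will "report higher levels of satisfaction, pleasure, and mood enhancements than smokers in the usual flavor EC condition", and that these responses will predict how far cigarettes are reduced. Section 9.0 (Aim 3) takes the data from EMA in the second week of SREC use and gives the analysis: "We will use linear mixed models to compare groups in terms of the EMA subjective reports and withdrawal symptoms". Empirical Bayes estimates from those models then enter a Poisson mixed model for later cigarette use.

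The Aim 3 power paragraph in section 12.0 starts from the number of reports expected before any SREC is dispensed, "that is likely to give about 30 random events and at least 21 smoke events at baseline across 120 participants", and describes this as "providing ample data for within- and between-subject analyses". It then gives a simulated example: "As an example, we can consider power for comparing responses from smoking reports to random prompts using simulation". The outcome is binary (whether the participant is alone), the ICC is 0.3 to 0.4, and the authors "estimated a logistic mixed effects model including a random subject effect and fixed effect comparing random prompts and smoking reports". The result is: "Under these assumptions, power exceeded 0.8 for an odds ratio of 1.2". Section 12.0 gives no power figure for the comparison of the two flavor groups on EMA ratings.

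**The concern.** The example and the planned Aim 3 test differ in four ways.

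| | Powered example (12.0) | Planned Aim 3 test (9.0) |
|---|---|---|
| Week | Baseline, before randomisation | Second week of SREC use |
| Reports | Cigarette reports and random prompts | SREC reports; withdrawal also at random times |
| Outcome | Binary context item | Satisfaction, pleasure, mood, withdrawal (linear mixed models) |
| Contrast | Between report types, same person | Between randomised groups |

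The last row matters most. In a within-person contrast the person effect largely cancels, so each extra report adds information. In a group contrast it does not cancel, and the number of people sets the limit. The predictive half of Aim 3 is also between persons, so the example does not cover it either.

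A reader who relies on this paragraph would expect Aim 3 to be sensitive to small group effects, and could take a non-significant flavor-group difference as more informative than it is.

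**Working it through.** **Inputs from section 12.0.** 30 random prompts and 21 smoking reports per person; 120 people; ICC 0.3 to 0.4; odds ratio 1.2; 60 randomised and 54 retained per arm. The Aim 4 paragraph supplies 10 SREC events per person ("20 smoking events and 10 SREC events, with 108 subjects") and a two-sided 0.05 test.

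**Assumptions added here.** The ICC is on the latent logistic scale; prevalence is 50% (none is stated); the two-sided 0.05 level also applies to Aim 3; the ICC given beside a binary item carries over to the continuous ratings.

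**Step 1. Person variance.** s² = ICC/(1−ICC) × π²/3, which is 1.41 at ICC 0.3 and 2.19 at ICC 0.4. The effect is ln 1.2 = 0.182.

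**Step 2. Reproduce the plan's figure.** For the within-person contrast, the information is N × E[v_r·v_s/(v_r+v_s)], where v_r and v_s are the binomial variances for 30 prompts and 21 reports, averaged over the person effect.

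| N | ICC | SE | Power, analytic | Power, simulated |
|---|---|---|---|---|
| 120 | 0.3 | 0.0589 | 0.87 | 0.87 |
| 120 | 0.4 | 0.0617 | 0.84 | 0.86 |
| 108 | 0.3 | 0.0621 | 0.84 | 0.83 |
| 108 | 0.4 | 0.0650 | 0.80 | 0.83 |

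The stated figure holds for its own contrast. It does need a mid-range prevalence: at an assumed 0.2 or 0.1, analytic power with 120 people is 0.77 to 0.79 or 0.65.

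**Step 3. Same odds ratio, group contrast.** SE² = 2 × (s² + 1/(m·pq))/n, with n people per arm, m reports each, and pq the mean of p(1−p) over the person effect (0.195 at ICC 0.3, 0.178 at ICC 0.4).

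Example, ICC 0.3, n = 54, m = 10: SE² = 2 × (1.410 + 0.513)/54 = 0.0712, so SE = 0.267. The ratio is 0.182/0.267 = 0.68, and power is Φ(0.68 − 1.96) + Φ(−0.68 − 1.96) = 0.10.

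| n per arm | m | Power, ICC 0.3 | Power, ICC 0.4 |
|---|---|---|---|
| 54 | 10 | 0.10 | 0.09 |
| 54 | 30 | 0.12 | 0.09 |
| 54 | 1000 | 0.13 | 0.10 |
| 60 | 10 | 0.11 | 0.09 |

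Simulation of the random-intercept logistic model with 54 per arm and 10 reports gives 0.093 and 0.098. A hundredfold increase in reports moves power by at most about two points.

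**Step 4. Detectable difference on the scale Aim 3 uses.** For a continuous rating, in total SD units, the difference detectable with 0.80 power is 2.80 × √[2 × (ICC + (1−ICC)/m)/n].

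Example, ICC 0.3, m = 10, n = 54: 2.80 × √(2 × 0.37/54) = 0.328.

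| n per arm | m | ICC 0.3 | ICC 0.4 |
|---|---|---|---|
| 54 | 10 | 0.33 | 0.37 |
| 60 | 10 | 0.31 | 0.35 |
| 54 | unlimited | 0.30 | 0.34 |
| 60 | unlimited | 0.28 | 0.32 |

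The range is therefore 0.31 to 0.37 SD, with a floor of 0.28 to 0.34 SD however many reports are made. For a binary response with 54 per arm and m = 10, the detectable group odds ratio is about 2.1 (ICC 0.3) to 2.4 (ICC 0.4).

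**Step 5. Baseline covariate.** Adjusting for a baseline mean that correlates ρ with the later mean multiplies the detectable difference by √(1−ρ²): 0.87 at ρ = 0.5 and 0.71 at ρ = 0.7, a reduction of 13% to 29%. The correlation is assumed.

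**The case against.** The best defence is that the plan makes no false claim about the flavor groups. The calculation is offered as an example, names its contrast, outcome and model, and reproduces. A reader might infer that the odds ratio of 1.2 is a miscalculation, or that the plan asserts power to detect it between arms. The documents support neither. The value of 0.1 in step 3 shows only that the figure does not transfer.

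A reader might also infer that attrition was ignored, because the paragraph mentions 120 people while section 12.0 says that every power calculation allows for 10% loss. That does not follow. The 120 describes expected baseline reports, the N used in the simulation is not stated, the 108 refers to the end of the study, and power at 108 is still about 0.80 to 0.84.

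The person-level limit is also not wholly absent. Just before the Aim 3 text, section 12.0 gives a detectable correlation of .262 with 108 people. A group difference of 2.80 × √(2/54) = 0.54 SD of person means corresponds to r = 0.54/√(0.54² + 4) = 0.26, the same limit. But that figure is offered for Aim 2 and is not connected to Aim 3.

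Finally, the sample size rests on the primary aims, so nothing here alters it. All of this stands, and it makes the matter one of a misplaced and missing power statement. It does not rescue the between-subject half of the claim about ample data: the event counts do not support it, and no other figure is given for Aim 3.

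**Conclusion.** The point holds as one about what the stated power applies to. The figure of above 0.8 at an odds ratio of 1.2 is right for a baseline-week, within-person contrast. It supports neither Aim 3's group comparison nor its prediction of cigarette reduction.

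With 54 to 60 per arm and about 10 SREC reports each, Aim 3 can detect about 0.31 to 0.37 total SD with 0.80 power. The values depend on borrowed inputs. The ICC comes from a passage about a binary item, and the documents give none for the ratings. The count of 10 comes from Aim 4 and does not fit withdrawal, which is also recorded at random prompts. The 54 is an end-of-study number applied to an EMA wave between the week 3 and week 4 visits, so 60 is the upper bound. The main conclusion, that more reports cannot make up for the number of people, does not depend on the exact inputs within these ranges.

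**What to change.** 1. In the Aim 3 paragraph of section 12.0, label the odds ratio of 1.2 as a within-person, baseline-week example, and stop citing event counts as support for between-subject analyses.

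2. Add the detectable group difference for the section 9.0 comparison: about 0.31 to 0.37 total SD at 0.80 power, two-sided 0.05, for 54 to 60 per arm, about 10 SREC reports per person and ICC 0.3 to 0.4 assumed to hold for the ratings, with a floor of 0.28 to 0.34 SD. If the team has ICCs for these ratings from its prior studies, use those. State that Aim 3 group differences will be reported with confidence intervals. Note that the predictive part is limited by about 108 people.

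3. For mood and withdrawal, which the baseline EMA week already records, add the person's baseline-week EMA mean as a covariate in the Aim 3 group model. The gain is roughly 13% to 29% at most, if the between-week correlation is 0.5 to 0.7. Satisfaction and pleasure with SREC have no pre-SREC counterpart, so this does not help there.

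The cost is a rewritten power paragraph with a less favourable figure, and one covariate from data already collected. Sample size, endpoints and procedures do not change.

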**Aim 4. Examine how patterns of use (e.g., contexts, timing) and subjective experience with SREC, differ from conventional cigarette use, and whether differences are associated with success in switching to SREC (giving up or reducing combustible and using SREC).** We will have baseline EMA data on smoking events and random time sampling of urges, mood, satisfaction with smoking, as well as context. Then we will have a week of EMA data on the second week of the instructed switch to SREC. We will compare EMA data during baseline to the SREC switch week on the following within subject factors: context of use (alone, with others; location – home; work; in public; presence of other smokers; time of day (e.g., first cigarette of the day); mood prior to use; mood after use; urge prior to use and at random time; satisfaction after use). We will use three-level (observations within weeks within subjects) linear mixed models for continuous outcomes (mood), logistic mixed models for binary outcomes (context), and survival mixed models for time to an event (first cigarette of the day). The main independent variable will be the indicator of EMA week (baseline/switch week) to test whether the outcomes vary by EMA week. We will also control for group (usual flavor/flavor choice) and examine whether the effect of EMA week varies by group. Analyses will also include sex and prior menthol use as covariates.

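### The within-week EMA contrasts are powered as if every participant had the same difference, and the analysis section specifies no model that lets that difference vary

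*Combined protocol and SAP*

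**What the plan says.** Section 12.0, Power considerations, Aim 3, introduces its calculation with "As an example, we can consider power for comparing responses from smoking reports to random prompts using simulation". It expects "about 30 random events and at least 21 smoke events at baseline across 120 participants", and "we assumed an intraclass correlation coefficient between 0.3 to 0.4". The simulations "estimated a logistic mixed effects model including a random subject effect and fixed effect comparing random prompts and smoking reports"; the null hypothesis is no difference between the two report types, and "power exceeded 0.8 for an odds ratio of 1.2".

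For Aim 4 the same section takes 20 smoking events and 10 SREC events per person, 108 people and the same ICC range. It gives a detectable odds ratio of 1.25 at power 0.8 (two-sided 0.05) and concludes that "we have excellent power to detect rather small differences for within-subject comparisons involving cigarette vs SREC reports". It names no model, and the ICC is the only clustering term.

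Section 9.0, Aim 3, specifies linear mixed models that compare the two randomised groups. Section 9.0, Aim 4, specifies three-level models with a week level inside subject, and the main independent variable is EMA week (baseline or switch). Neither gives a model or random effects for smoking report versus random prompt, or for cigarette versus SREC report, within a week.

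Section 3.0, Aim 4, hypothesises that "subjects who have fewer differences in patterns and experiences between cigarettes and SREC will reduce cigarettes more and maintain SREC use longer". For the Aim 1 time trends, section 9.0 does specify random effects so that participants may differ.

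**The concern.** A random subject effect lets people differ in their overall level, for example in how often they are alone. A single fixed contrast then gives everyone the same log odds ratio between report types. If people differ in that contrast, the standard error leaves out the between-person variance of the contrast. The interval for the average difference is then too narrow, and a true average of zero is rejected more often than 5%.

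The Aim 4 hypothesis needs the cigarette/SREC difference to vary between people, because it uses that difference to predict who reduces. A model with a common contrast contradicts this premise and yields no person-specific contrast to carry into that analysis.

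At stake are the error rate of any within-week event-type or product test fitted this way, and the detectable odds ratios quoted for Aims 3 and 4.

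**Working it through.** **Inputs from section 12.0.** Aim 3 layout: 120 people, 30 random prompts and 21 smoking reports each, odds ratio (OR) 1.2. Aim 4 layout: 108 people, 20 cigarette and 10 SREC reports each, OR 1.25, two-sided 0.05. ICC 0.3 to 0.4.

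**Assumptions, because the documents are silent.** The ICC is read on the latent logistic scale, so subject variance = ICC/(1−ICC) × π²/3, which is 1.41 to 2.19. The baseline probability is 0.5 for a person with zero subject effect (0.3 was also tried for the power figures). Tau, the between-person SD of the log odds ratio, ranges from 0 to 1.0.

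**Step 1: the plan's own figures, tau = 0.** The random-intercept logistic model was fitted by maximum likelihood to 1,000 simulated data sets per cell.
- Aim 3, OR 1.2: power 0.84 to 0.88 with 120 people and 0.80 to 0.84 with 108. The stated figure, above 0.8, is reproduced.
- Aim 4, OR 1.25: power 0.75 at ICC 0.3 and 0.71 to 0.72 at ICC 0.4, against 0.8 stated. Under these assumptions 80% power needs an OR of about 1.27 to 1.28.

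Check by formula. Information per person is I = E[p(1−p)] × n1·n2/(n1+n2). At ICC 0.3, E[p(1−p)] is 0.195.
- Aim 3: I = 0.195 × 630/51 = 2.41; SE = 1/√(120 × 2.41) = 0.0588; ln 1.2 = 0.182; power = Φ(0.182/0.0588 − 1.96) = 0.87.
- Aim 4: I = 0.195 × 200/30 = 1.30; SE = 1/√(108 × 1.30) = 0.0844; ln 1.25 = 0.223; power = Φ(0.223/0.0844 − 1.96) = 0.75.

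**Step 2: type I error of the intercept-only test when the contrast varies.** The ratio of true to model variance is 1 + tau² × I, so the rejection rate is about 2 × [1 − Φ(1.96/√(1 + tau² × I))]. Example, Aim 3 at tau 0.5: 1 + 0.25 × 2.41 = 1.60; 1.96/√1.60 = 1.55; rate 12%.

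| tau | Aim 3: formula (ICC 0.3) | Aim 3: simulated (ICC 0.3 / 0.4) | Aim 4: formula (ICC 0.3) | Aim 4: simulated (ICC 0.3 / 0.4) |
|---|---|---|---|---|
| 0 | 5.0% | 4.6% / 4.5% | 5.0% | 5.1% / 5.1% |
| 0.25 | 6.8% | 7.0% / 7.2% | 5.9% | 5.8% / 5.8% |
| 0.5 | 12.2% | 12.6% / 12.7% | 8.9% | 9.0% / 8.5% |
| 0.75 | 20.2% | 21.5% / 20.6% | 13.6% | 13.4% / 12.9% |
| 1.0 | 28.8% | 30.1% / 28.1% | 19.6% | 19.8% / 18.7% |

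The simulated rates use 2,000 data sets per cell and a true mean difference of zero.

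**Step 3: a person-specific contrast in the model.** ICC 0.3, 400 data sets per cell. Type I error was 3.3% to 5.5% over both layouts and tau 0.5 to 1.0 (Monte Carlo SE about 1.1 points). The power check uses SE = √((1/I + tau²)/N).

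| tau | Aim 3, OR 1.2: simulated (formula) | Aim 4, OR 1.25: simulated (formula) |
|---|---|---|
| 0.5 | 0.73 (0.69) | 0.65 (0.63) |
| 0.75 | 0.54 (0.52) | 0.53 (0.52) |
| 1.0 | 0.43 (0.39) | 0.45 (0.41) |

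By the same formula, the OR detectable with 80% power is exp(2.80 × SE). At tau 0.5 to 1.0 that is about 1.23 to 1.36 in the Aim 3 layout and 1.31 to 1.43 in the Aim 4 layout, against 1.2 and 1.25 stated.

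**The case against.** The strongest reply is that the quoted model belongs to a power illustration, not to the declared analysis, and that the plan does allow heterogeneity where it is explicit about it. Both statements are correct, and they limit the point. Four stronger readings are tempting, and the documents do not support them.

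- A reader might infer that the final event-type and product analyses will use the intercept-only model. The documents do not say so. They leave the random effects for these contrasts unspecified.
- A reader might infer that false positives would accumulate over the context, mood and urge outcomes listed under Aim 4. Those outcomes are compared between EMA weeks. A random effect for week within subject lets each person's week difference vary, so that test is protected. It does not protect a contrast made within one week.
- A reader might infer a fixed inflation, such as two to five times the nominal 5%. That range needs tau of about 0.42 to 0.93 in the Aim 3 layout and 0.57 to 1.27 in the Aim 4 layout. At tau 0.25 the rate is only 5.8% to 7.2%, and the documents give no tau.
- A reader might infer that the Aim 3 power claim fails unless everyone has an identical effect. A small tau does little harm: at tau 0.25 and ICC 0.3 the formula gives SE √((1/2.41 + 0.0625)/120) = 0.063 and power of about 0.82.

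It is also true that the Aim 4 hypothesis speaks of cigarette/SREC differences only. For smoking reports versus random prompts, heterogeneity is plausible but is not asserted by the plan.

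What remains is that the only model stated for a within-week contrast assumes no heterogeneity, nothing in section 9.0 replaces it, and the quoted power rests on it.

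**Conclusion.** The point holds in a limited form. The power figures for the within-week contrasts assume no person-to-person variation in the contrast, and the analysis section does not provide for any, while the Aim 4 hypothesis presumes it for cigarettes versus SREC.

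The consequence depends on a tau that the documents do not give. Over the assumed range of 0.25 to 1.0 it runs from slight to serious, both for the error rate of an intercept-only test and for the power of a test that allows variation. The sizes also rest on the latent-scale reading of the ICC and about 50% prevalence. The post-fix power figures were run at ICC 0.3 only.

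Separately, the Aim 4 power falls 5 to 9 points short of 0.8 even at tau = 0 under these assumptions, which is a further reason to redo it.

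These are EMA aims. The primary endpoint and the EMA-week test do not depend on this point, so the change is advisable rather than critical.

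**What to change.** In section 9.0, state the model for each within-week contrast (smoking report versus random prompt, cigarette versus SREC report) and include a subject-level random slope for that contrast. Name subject-clustered robust standard errors as the fallback if the model does not converge. The random slope also supplies the person-specific contrasts that the second half of Aim 4 needs.

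In section 12.0, re-run both power calculations over a range of slope SDs, preferably including an estimate from the team's current data that supplied the ICC. State the baseline probability and the ICC scale used, and restate the detectable odds ratios.

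The cost is one extra random term, a re-run of an existing simulation and somewhat less favourable detectable odds ratios. No new data are needed.

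### The Aim 4 power of 0.80 for an odds ratio of 1.25 becomes about 0.71–0.75 under the described model with the usual ICC scale, and the inputs that decide this are not stated

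*Combined protocol and SAP*

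**What the plan says.** The Aim 4 power paragraph in Section 12.0 covers the switch week, when a participant may report both products. Its inputs are: "If we assume, conservatively, 20 smoking events and 10 SREC events"; a sample described as "with 108 subjects (allowing for 10% attrition"; and "an ICC between 0.3 and 0.4". It concludes that "we can detect an odds ratio of 1.25 with power = .8 on a two-tailed .05 test", and then calls the power for small within-person product differences excellent.

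That paragraph names no model. The preceding Aim 3 paragraph does. It considers a binary outcome (being alone or not) with the same ICC range, and reports that the authors "estimated a logistic mixed effects model including a random subject effect and fixed effect comparing random prompts and smoking reports". Its result is "Under these assumptions, power exceeded 0.8 for an odds ratio of 1.2".

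Neither paragraph gives the outcome prevalence, the scale of the ICC, or whether the odds ratio is subject-specific or marginal. Section 9.0 (Aim 4) plans logistic mixed models for binary context outcomes but adds nothing on these points.

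**The concern.** The Aim 4 inputs are explicit enough to recompute. With the model described for Aim 3 and the usual ICC convention for a logit model, they do not give 0.80.

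What is at stake is how Aim 4 results will be read. If readers believe that an odds ratio of 1.25 was well covered, they may take a null product comparison as evidence of no difference. Section 9.0 lists outcomes such as location and the presence of other smokers. The documents give no frequencies for these, but some could lie well away from 50%, and power falls as they do.

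**Working it through.** **Inputs from Section 12.0.** N = 108; n0 = 20 smoking and n1 = 10 SREC events per subject; ICC 0.3 to 0.4; odds ratio 1.25, so ln(1.25) = 0.2231; the test is "on a two-tailed .05 test", so the critical value is 1.96.

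**Assumptions, because the plan is silent.** Aim 4 uses the random-intercept logistic model described for Aim 3; the odds ratio is that model's fixed effect, hence subject-specific; prevalence is 50% first, then lower.

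**Formulas.** With p the subject's own event probability and E[·] the average over the random subject effect:

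- SE(ln OR) ≈ 1/√(N × n0·n1/(n0+n1) × E[p(1−p)])
- N × n0·n1/(n0+n1) = 108 × 200/30 = 720
- Power = Φ(0.2231/SE − 1.96)
- Odds ratio detectable with power 0.80 = exp((1.96 + 0.8416) × SE)

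**Step 1: can the plan's 0.80 be reproduced?** Yes, if the subject variance is set to ICC/(1−ICC), that is, a residual variance of 1. At 50% prevalence this gives 0.81 (ICC 0.3) and 0.80 (ICC 0.4).

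**Step 2: usual latent scale.** The subject variance is ICC/(1−ICC) × π²/3, which is 1.41 at ICC 0.3 and 2.19 at ICC 0.4.

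| Prevalence | ICC | E[p(1−p)] | SE | Power at OR 1.25 | OR for power 0.80 |
|---|---|---|---|---|---|
| 50% | 0.3 | 0.195 | 0.0844 | 0.75 | 1.27 |
| 50% | 0.4 | 0.178 | 0.0884 | 0.71 | 1.28 |
| 20% | 0.3 | 0.132 | 0.103 | 0.59 | 1.33 |
| 20% | 0.4 | 0.122 | 0.107 | 0.55 | 1.35 |

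The first row in full: 720 × 0.195 = 140.4; SE = 1/√140.4 = 0.0844; 0.2231/0.0844 = 2.64; Φ(2.64 − 1.96) = 0.75.

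The 20% rows move slightly with the product to which the 20% refers and with the direction of the effect. Power is then about 0.54 to 0.60, and the detectable odds ratio about 1.33 to 1.36.

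**Step 3: simulation.** Full maximum-likelihood fits to 6,000 simulated datasets per setting, at 50% prevalence, give 0.745 (ICC 0.3) and 0.717 (ICC 0.4), in agreement with the formula.

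**Step 4: other readings (108 subjects unless stated, 50% prevalence).**

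| Reading | ICC 0.3 | ICC 0.4 | Fits the text? |
|---|---|---|---|
| One-sided 0.05 | 0.84 | 0.81 | No: two-tailed is stated |
| 120 subjects | 0.80 | 0.76 | No: 108 is stated |
| ICC ignored | 0.85 | 0.85 | No: an ICC is stated |
| Residual variance 1 | 0.81 | 0.80 | Not excluded, but not the usual logit scale |
| Observed-scale ICC, subject-specific OR | 0.71 | 0.64 | Not excluded |
| Marginal OR, latent ICC | 0.92 | 0.94 | Does not match the fixed effect of the named model |

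**Step 5: subjects needed.** On the usual latent scale at 50% prevalence, an odds ratio of 1.25 needs about 122 subjects (ICC 0.3) to 134 (ICC 0.4) for power 0.80.

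**The case against.** The strongest reply is that the Aim 4 paragraph fixes neither the ICC scale nor the type of odds ratio, so the shortfall comes partly from choices the plan did not make. This stands in part. With residual variance 1 the stated 0.80 returns across the whole ICC range at 50% prevalence, and a marginal odds ratio of 1.25 gives more than 0.80 there. A reader might therefore infer from the table that power can never exceed 0.75; the documents do not support that without the stated conditions. Still, residual variance 1 is not the usual scale for a logit model, and even on it power falls to about 0.73–0.76 at 30% prevalence. The fixed effect of a random-intercept logistic model is subject-specific, not marginal.

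Two other inferences are tempting and should not be drawn.

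- A reader might infer that attrition was left out, because 120 subjects give 0.80 at ICC 0.3. The text says 108 and says that 10% attrition was assumed in every power calculation, and 120 subjects give only 0.76 at ICC 0.4.
- A reader might infer that the error is confined to Aim 4, because the latent-scale method gives 0.87 and 0.84 for Aim 3 (120 participants, 30 random prompts, 21 smoking events, odds ratio 1.2). The plan claims only that Aim 3 power exceeded 0.8. The residual-variance-1 scale also satisfies that, at 0.92 and 0.91, so the check cannot show which method was used.

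It is also fair to say that the consequence is small: 1.27–1.28 is not far from 1.25.

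**Conclusion.** The point holds conditionally. Given a random-intercept logistic model, a subject-specific odds ratio and a latent-scale ICC, power for an odds ratio of 1.25 falls short of the stated 0.80 by 5 to 9 percentage points even at the most favourable prevalence, and by about 20 to 26 points at 20%. Because the plan omits the inputs that would confirm or correct its figure, the claim cannot be verified as written.

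The shortfall at 50% prevalence is modest. It concerns a within-subject EMA aim; the sample of 120 was set on the primary aims and is not affected.

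**What to change.** In the Aim 4 power paragraph of Section 12.0, state the assumed prevalence, the scale of the ICC, whether the odds ratio is subject-specific or marginal, and the model or simulation used. Then restate the figure to match.

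If the usual latent scale and a subject-specific odds ratio are intended, either give power of about 0.71–0.75 for an odds ratio of 1.25 at 50% prevalence, or say that power 0.80 is reached at about 1.27–1.28 (50%) and about 1.33–1.36 (20%). If another scale or a marginal odds ratio was used, say so and show the power over a range of prevalences. In either case, tone down the description of the power as excellent.

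The cost is a few sentences, one rerun of the calculation and a slightly less favourable figure. Design, sample size and conduct do not change.
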